10.2 Sample Size Calculations

The primary endpoint on which sample size estimates are based is the change in the overall NIH-CPSI score from baseline (randomization) to six (6) weeks. The total score has a potential range of 0 – 43 points. For each of the two primary comparisons--ciprofloxacin (CIPRO®) versus no ciprofloxacin (CIPRO®) or tamsulosin hydrochloride (FLOMAX®) versus no tamsulosin hydrochloride (FLOMAX®), we desire adequate numbers of participants to detect a difference of four (4) points in the change from baseline. We require 80% power to detect the specified difference between groups at a two-sided $\alpha = 0.05$ level of significance using a two-sample t-test. After adjustments to allow for possible dilution of statistical power due to interaction in the factorial design (50% increase), withdrawal (15% increase), clustering within Clinical Center (15% increase), a total of 184 participants or $184/4 = 46$ participants per arm will be required. Total required sample sizes for alternative differences are shown in the table below.

Δ	Trial Design	Total Sample Size using sd of change $\sigma = 6.76$
3 points	2 arms	216 (108/arm)
	3 arms	420 (140/arm)
	4 arms	644 (61/arm)
	2 x 2	324 (81/arm)
4 Points	2 arms	122 (61/arm)
	3 arms	237 (79/arm)
	4 arms	368 (92/arm)
	2 x 2	184 (46/arm)
5 Points	2 arms	80 (40/arm)
	3 arms	156 (52/arm)
	4 arms	240 (60/arm)
	2 x 2	120 (30/arm)

In addition, for each individual treatment arm of 46 subjects, the width of a 95% confidence interval for adverse event and other rates will be no wider than $\pm 15.0\%$. It is expected that these 184 participants can be accrued within approximately ten (10) months. Allowing for an additional twelve (12) weeks of follow-up on all participants, the entire study should require fourteen (14) months for completion.

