2.3 Study Endpoints

2.3.1 *Primary Endpoint*

The primary endpoint to be used for efficacy evaluation is the overall NIH-CPSI (Appendix A) (scale of 0-43). The change in this score from baseline to six (6) weeks will be calculated for each participant and compared among treatment groups (see Section 10.3 for details of primary endpoint analysis).

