7 TRIAL TESTS AND PROCEDURES

7.1 Procedural Summary

Prior to the baseline screening, potential participants must have had symptoms of discomfort or pain in the pelvic region for at least a three (3) month period within the last (6) months.

This study is comprised of phases for each participant: i) the *screening phase* and ii) the *treatment and follow-up phase*. The screening phase, which assesses a participant's eligibility via inclusion, exclusion and deferral criteria, will consist of two baseline visits no more than three (3) weeks and no less than seven (7) days apart. Any candidate failing any of the inclusion or exclusion criteria, during either of the screening visits will be considered ineligible for the protocol. Some participants may have their entry into the study deferred to a later time based on the results of the deferral criteria.

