7.2 Screening Visit #1

The first screening visit should occur no more than three (3) weeks and no less than one (1) week prior to randomization. During this screening visit, the forms and procedures listed below will be completed. If a participant fails to meet any of the study eligibility criteria, based on the data collected during this visit, he would not be required to complete the physical examination, urinalysis, or urine culture for the purposes of the study. (See **Appendix C**).

1. *Eligibility Criteria.*

Each participant will complete a preliminary screening form that checks whether he meets the initial inclusion/exclusion/deferral criteria. (These criteria will be verified at the second baseline visit.)

2. *Participant Contact Information.*

Participants will be asked to provide the clinical center with their address, phone number, primary care physician, and the name and address of two other contacts. This information will be stored at the CRC and available only to selected study personnel. Participants who have previously enrolled in the CPC will be asked only to update the previous information.

3. *Participant Medical History.*

Each participant will provide the research staff with his general medical history and specific genitourinary medical history. In particular, the participant will be asked to provide information regarding his disease and surgical histories.

4. *Participant Symptom Index.*

[figure not shown]
Each participant will provide the research staff with an assessment of his discomfort/pain by completing the full NIH-CPSI.

5. *Physical Examination.*

Each participant will undergo a focused physical examination. This examination will include an abdominal exam, external genital exam, rectal exam, prostate exam, and perineal exam. Participants enrolled in the CPC who have completed a physical examination within one (1) month of enrolling in the RCT, will not be asked to complete another physical examination.

6. *Urinalysis, Urine and EPS Specimens for Microscopy and Culture.*

Each participant will provide the research staff with three (3) urine specimens and an EPS (expressed prostatic secretion) specimen for analysis and culture. The urine specimen will be collected via the classic “four-glass test” (FGT) described in Meares and Stamey(28). The FGT will be attempted one time only at each of Screening Visit #1 and at the six (6) week clinic visit.

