7.3 Screening Visit #2

Participants who still meet all eligibility criteria at this visit will complete the questionnaires and/or undergo the examinations described below, and will continue on to randomization (Section 7.4).

1. *Eligibility Checklist*.

An eligibility checklist confirming that the participant still meets all eligibility criteria will be completed by the RC prior to randomization.

2. *Demographic Questionnaire.*

Each participant will provide the research staff with his demographic information, including date of birth (age), race, marital status, socioeconomic status, level of education.

3. *Concomitant Medications.*

The research staff will record the medications currently being taken by the participant. Participants will be asked to recall their medications if they fail to bring them to the second screening visit.

4. *Participant Symptom/Impact/General Quality of Life Index.*

Each participant will provide the research staff with an assessment of his discomfort/pain by completing the NIH-CPSI. In addition, participants will complete the MOS SF-12, a general Quality of Life Index.

5. *1-day Voiding Log Supplies and Directions.*

A 24-hour voiding log will be collected and reviewed for completion for each participant.

6. *Uroflow and Post Void Residual.*

Participants will undergo urodynamic testing at screening visit #2. The research staff will measure and record participants total voided volume, peak flow, average flow and post-void residual.

7. *Semen Sample Collection.*

A semen sample will be collected and cultured for localized pathogens. Participants are permitted to refuse to provide a semen sample. It is also acceptable if a participant is unable to provide a semen sample. However, participants not providing a semen sample, for whatever reason, must have provided at least one of either an EPS or VB3 sample during screening visit #1.

8. *Medication Diary.*

Participants will be required to maintain a medication diary to record any changes in medication. Participants will also be asked to record all possible adverse events.

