8.5 Unmasking of Treatment

At the end of Baseline Screening Visit #2, participants will be randomized following a randomization schedule generated by the DCC prior to study initiation. Neither the Investigator nor the investigational site personnel will know the treatment group to which any participant is randomized. Unmasking of treatment assignment is anticipated to be an extremely uncommon occurrence and is strongly discouraged. If there is a serious adverse event, which is thought by the clinical site staff to be possibly or probably related to the coded medication, the clinical site staff, when necessary for the safety of the participant, may be permitted to request unmasking of treatment group assignment. Approval to unmask will be granted by the study's medical monitor in collaboration with the clinical site's Investigator.

The clinical site staff should contact the On Site Investigator, who would promptly page the medical monitor. If decided that unmasking is appropriate, the medical monitor should immediately contact the University of Pennsylvania Investigational Drug Service (IDS) with a request to unmask the treatment group assignment. The IDS Pharmacist will report the treatment arm to the On Site PI (or designee). The clinical site staff must report the unmasking to the DCC via within one (1) working day, to be followed by submission of a detailed report to the DCC within three (3) working days of the unmasking event. The clinical site must also promptly notify their IRB of the unmasking occurrence in accordance to reporting requirements.

In accordance to the ICH *Guideline for Industry Clinical Safety Data Management's* section on expedited reporting: "Although it is advantageous to retain the blind for all patients prior to final study analysis, when a serious adverse event is judged reportable on an expedited basis, it is recommended that the blind be broken only for that specific patient by the sponsor even if the investigator has not broken the blind. It is also recommended that, when possible and appropriate, the blind be maintained for those persons, such as biometrics personnel, responsible for analysis and interpretation of results at the study's conclusion." For the purposes of this protocol, if dissemination of this unmasking information from the Sponsor to the Licensed Product Holders is requested, a collaborative discussion/process is appropriate.

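### Two NIH-CPSI totals are collected before randomization, but the primary change uses only the one at randomization, with no baseline term in the model: a modest, avoidable loss of precision

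*Protocol*

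**What the plan says.** Section 2.3.1 makes the total NIH-CPSI (0–43) the primary endpoint: "The change in this score from baseline to six (6) weeks will be calculated for each participant". Section 10.2 is more specific and takes the "change in the overall NIH-CPSI score from baseline (randomization) to six (6) weeks". Section 8.5 fixes the moment: "At the end of Baseline Screening Visit #2, participants will be randomized". On the plain reading, baseline is the Visit 2 total.

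The index is also completed earlier. Section 7.1 describes "two baseline visits no more than three (3) weeks and no less than seven (7) days apart". At Visit 1 each man gives an "assessment of his discomfort/pain by completing the full NIH-CPSI" (section 7.2), and at Visit 2 an "assessment of his discomfort/pain by completing the NIH-CPSI" (section 7.3). The schedule in Appendix C marks the form at both visits.

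Section 10.3.2 analyses the week 0 to week 6 change by linear regression, with treatment and a random centre effect. Adjustment for prognostic factors is left to secondary analyses. No section gives the Visit 1 total a role beyond screening.

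**The concern.** The symptom items in Appendix A ask about the last week. Visits at least seven days apart therefore sample different weeks of the same man's symptoms. A change score with no baseline adjustment carries the whole short-term fluctuation of the one baseline score it starts from. A second pre-treatment score is already on file and could reduce that part of the noise. Both scores precede randomization, so using them cannot bias the comparison of arms. What is at stake is the width of the intervals for the two primary contrasts, ciprofloxacin against none and tamsulosin against none.

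**Working it through.** **1. The plan's own figure.** Inputs from section 10.2: difference 4 points, SD of change 6.76, two-sided alpha 0.05, 80% power, two-sample t-test; increases of 15% for withdrawal, 15% for clustering and 50% for interaction.

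- The exact t-test needs 46 per group.
- 46 × 1.15 × 1.15 = 60.8, so 61 per group, or 122 in two arms.
- 122 × 1.5 = 183, rounded up to a multiple of four: 184.

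The same route gives the stated 216 and 324 (3 points) and 80 and 120 (5 points). The figure is sound.

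**2. Formulas.** Let B1, B2 and Y be the Visit 1, Visit 2 and week 6 totals, with equal variances and correlations r12 (B1, B2), r2 (B2, Y) and r1 (B1, Y). Residual variances, each divided by the variance of the planned change Y − B2, which is proportional to 2(1 − r2):

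- Change from the mean of B1 and B2: [(1 + r12)/2 + 1 − r1 − r2] / [2(1 − r2)].
- B2 as covariate: (1 − r2²) / [2(1 − r2)] = (1 + r2)/2.
- B1 and B2 as covariates: (1 − R²) / [2(1 − r2)], with R² = (r1² + r2² − 2·r12·r1·r2)/(1 − r12²).

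Averaging gains only while r2 − r1 < (1 − r12)/2.

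**3. Assumed patterns.** The protocol gives no correlation and no source for 6.76, so every row is an assumption. The entries are variance ratios to the planned analysis.

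| r12 / r2 / r1 | Averaging | B2 covariate | Both covariates | Both vs B2 alone |
|---|---|---|---|---|
| 0.6 / 0.6 / 0.6 | 0.750 | 0.800 | 0.688 | 14% less |
| 0.7 / 0.6 / 0.55 | 0.875 | 0.800 | 0.759 | 5% less |
| 0.8 / 0.6 / 0.55 | 0.938 | 0.800 | 0.783 | 2% less |
| 0.8 / 0.6 / 0.5 | 1.000 | 0.800 | 0.799 | 0.2% less |
| 0.9 / 0.6 / 0.5 | 1.062 | 0.800 | 0.789 | 1% less |

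Worked example, second row. Averaging: (0.85 + 1 − 1.15)/0.80 = 0.70/0.80 = 0.875. Both covariates: R² = (0.3025 + 0.36 − 0.462)/0.51 = 0.393, and 0.607/0.80 = 0.759. Against B2 alone: 0.759/0.800 = 0.948.

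**4. Entry rule.** I simulated a total of at least 15 at both visits (assumed mean 23, SD 7 before selection). With equal correlations of 0.4 to 0.8:

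- averaging gives ratios of 0.76–0.78;
- adding B1 to a B2 covariate removes a further 6–18% of residual variance.

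In the moderate decay row that further gain is about 4%. Over these equal-correlation patterns and the four decay rows of the table, both covariates together cut the variance by 14–29% against the planned analysis. Most of that comes from adjusting for baseline at all.

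**5. On the scale of the trial.** With 15% loss, 92 × 0.85 ≈ 78 men per side. The half-width of the 95% interval is 1.96 × SD × √(2/78), before any allowance for clustering or interaction.

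- Planned, SD 6.76: 2.12 points.
- Averaging, equal correlations, SD 6.76 × √0.75 = 5.85: 1.84 points.
- Averaging, moderate decay, SD 6.76 × √0.875 = 6.32: about 1.98 points.

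At 46 per group, power by the normal approximation is 81% as planned, and 91% at the 25% ceiling.

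**The case against.** The strongest reply is that nothing here is wrong. Taking baseline at randomization is conventional, sections 10.2 and 10.3.2 agree with each other, and analysis details are deferred to the Data Analysis and Monitoring Plan. This stands as far as it shows that there is no error. But section 10.2 does name the baseline, so a plan that averaged the two scores would depart from it.

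Second, averaging is not reliably better. Visit 1 lies seven to nine weeks before week 6, and if it predicts week 6 markedly worse while the two screening scores agree closely, averaging gains nothing or loses. This stands, and it is why covariates are preferred to a plain mean. In the decay rows even Visit 2 alone as covariate does better than averaging.

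Third, no conclusion is shown to be at risk. With 78 per side and SD 6.76, power for 4 points is about 96% before clustering and interaction, and about 93% after a 15% clustering allowance. That also stands; it limits the point to efficiency.

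Fourth, the SD of 6.76 and the 4-point target refer to change from randomization. With Visit 2 in the model, analysing the change or the week 6 score gives the same treatment contrast, so the target is unchanged. Only the residual SD needs restating.

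A reader might take the quotation in the Introduction about highly variable symptoms as proof of week-to-week variation within a man. It describes difficulties of trials in nonbacterial prostatitis and may equally mean variation between men. No within-man figure is given.

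**Conclusion.** The point holds as a modest efficiency gain left unused. The Visit 1 total is collected and not used for efficacy, and the primary model does nothing to recover the fluctuation in the single baseline. The gain from averaging runs from 25% less variance under equal correlations, through about 12% with moderate decay, to nil or a loss of about 6% in unfavourable patterns. Using both scores as covariates was better than the planned analysis in every pattern tried, but the share owed to Visit 1 beyond Visit 2 is only about 0–18%, and about 4% with moderate decay. All of this rests on assumed correlations.

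Three stronger inferences are not supported:

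- **Bias between arms.** Both scores precede randomization, and the entry rule acts alike on all arms.
- **A wrong or inadequate sample size.** 184 follows exactly from the stated inputs.
- **A dependable 25% gain.** That figure is the equal-correlation ceiling, before the effect of the entry rule.

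**What to change.** In section 10.3.2, enter both the Screening Visit 1 and Visit 2 NIH-CPSI totals as covariates in the primary linear model, keeping treatment and the random centre effect. Where the Visit 1 total is incomplete, use the Visit 2 total alone, so that no man drops out of the analysis. If an unadjusted change score is preferred, sections 2.3.1 and 10.2 may instead define baseline as the mean of the two totals, accepting that this can gain nothing or lose under strong decay. Leave the entry rule as it is, and report the planned change from randomization as a sensitivity analysis.

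The cost is wording and no new data, since both forms are already scheduled. The downsides are small: the Visit 1 score is up to three weeks older, and the baseline definition and the basis of the SD must be restated before unblinding.

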10.3 Intent-to-Treat Analyses and Missing Data

An *intent-to-treat* analysis, for which all available data on all randomized participants are included, will be used for the primary comparison of treatments. All attempts will be made to keep missing data to a minimum and participants who withdraw from treatment will be encouraged to continue on study in order to provide complete follow-up information. However, it is expected that up to 15% of the randomized participants may withdraw prior to the final assessment of response at six (6) weeks. The loss of power due to withdrawals is incorporated into sample size calculation for the primary endpoint above. For secondary endpoints involving comparisons of response rates, these participants will be included in the denominator. The characteristics at time of randomization for those participants without complete follow-up will be examined; however, there will be limited statistical power to detect any but major differences between these participants and those with complete follow-up. In addition, in order to assess the potential biases introduced by differential withdrawal among treatment arms, a comparison of withdrawal rates and time to withdrawal will be included as an ancillary analysis to the primary endpoint comparison. Additional details of the evaluations of withdrawals are provided in the section regarding longitudinal data analysis below.

10.3.1 *Data Safety Monitoring and Interim Analysis*

Standard monitoring for adverse events and data quality will be performed on a regular basis. Details of frequency and content of monitoring will be outlined in the DAMP. These analyses will be presented to the External Advisory Committee.

Due to the expected rapid accrual and brief length of follow-up, no interim analysis comparing efficacy among groups will be conducted.

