8.6 Participant Withdrawal

It is expected that up to 10% of participants may drop out of the trial due to side effects or lack of efficacy prior to the six (6) week endpoint. However, all attempts will be made to get complete data on all participants, including those who cease treatment prior to six (6) weeks, in order to conduct the primary intent-to-treat analysis. It is expected that a maximum of 15% of participants will withdraw completely from treatment AND follow-up prior to six (6) weeks.

Under certain circumstances, a study participant may have his treatment terminated prior to the six (6) week clinic visit. These circumstances include: unacceptable concomitant medications/treatments, unacceptable adverse events as determined by the Principal Investigator (PI), participant dissatisfaction with treatment, or participant disinterest in continued study participation. In addition, any participant who acquires a serious or life-threatening medical condition while participating in the study may have the study treatment terminated early at the discretion of the PI. A participant may also undergo early study termination because of a change of residence outside the driving distance of the CPCRn network.

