The analysis comparing the mean change in NIH-CPSI overall score from 0 to 6 weeks among treatment arms will utilize a linear regression model (equivalent to a 2-way analysis of variance) with a random effect to allow for clustering on clinical center. Standard regression diagnostics will be used to assess model adequacy and examine potential outlying or influential data points. Secondary analyses of the primary endpoint will include multivariable regression models to evaluate whether observed treatment differences, if any, can be partially accounted for by baseline differences in prognostic factors between treatment arms. Profiles of the overall NIH-CPSI score over time will also be compared among treatment groups using random effects regression models (35).

Secondary Analyses

A number of secondary analyses will be conducted, both to evaluate the secondary symptom-related outcomes and to supplement the primary endpoint comparison. Evaluation of some of the secondary outcomes will involve comparison of binary outcomes or response rates among groups. These endpoints may include the global assessment of change, change in white blood cell counts in the four-glass test, subscores of the NIH-CPSI, MOS SF12, and voiding frequency measured by a one day voiding log.

For example, one type of response will be defined based on the participant reported global assessment of change as measured at six (6) weeks or withdrawal, whichever comes first. A seven point scale will be used: 0) markedly worse; 1) moderately worse; 2) slightly worse; 3) no change; 4) slightly improved; 5) moderately improved; and 6) markedly improved. Participants who answer either 5) moderately or 6) markedly improved on this question will be considered to be responders. For this endpoint, participants who withdraw from the study for any reason (e.g. adverse events or participant choice) prior to six (6) weeks will be considered treatment non-responders. Following standard “intent-to-treat” methods, these withdrawals will be included in the denominator of the response rates for evaluation. This outcome will also serve as a validation for the primary endpoint above.

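### The primary comparison is labelled intent-to-treat, but the model in 10.3.2 can use only men with a week-6 NIH-CPSI, so it is in effect a complete-case analysis

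*Protocol*

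**What the plan says.** Section 10.3 describes the primary analysis as intent-to-treat, "for which all available data on all randomized participants are included, will be used for the primary comparison of treatments". Section 2.3.1 defines the endpoint: "The change in this score from baseline to six (6) weeks will be calculated for each participant and compared among treatment groups". Section 10.3.2 gives the model: "The analysis comparing the mean change in NIH-CPSI overall score from 0 to 6 weeks among treatment arms will utilize a linear regression model". It is equivalent to a two-way analysis of variance, with a random effect for centre.

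On losses, section 10.3 says that "it is expected that up to 15% of the randomized participants may withdraw prior to the final assessment of response at six (6) weeks", and for the primary endpoint adds: "The loss of power due to withdrawals is incorporated into sample size calculation for the primary endpoint above". Section 8.6 gives two rates. It expects that "up to 10% of participants may drop out of the trial due to side effects or lack of efficacy" before week 6, and separately that "a maximum of 15% of participants will withdraw completely from treatment AND follow-up prior to six (6) weeks", with no reason attached to the second figure. Sections 8.6 and 10.3 both say that men who stop treatment will be encouraged or pursued to stay in follow-up.

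Secondary endpoints do have a rule. Withdrawals stay in the denominator of response rates (10.3), and they count as non-responders on the global assessment (10.3.2). Random-effects models of the NIH-CPSI profile are planned in 10.3.2, but not as the primary comparison. Appendix C schedules the NIH-CPSI at week 3 and at the early-stop visit (Visit 98).

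**The concern.** A model for the 0-6 week change cannot use a man who has no week-6 score. The label therefore promises more than the model delivers. Raising the sample size for withdrawal restores precision but does nothing about bias. Section 8.6 expects some men to leave because of side effects or lack of efficacy. Those reasons are related to outcome and may differ between treatment groups, in which case the remaining men are no longer comparable as randomised.

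Section 10.3 anticipates this. It lists a comparison of baseline characteristics (with admittedly limited power) and comparisons of withdrawal rates and times; 10.3.2 adds Kaplan-Meier, logrank and Cox methods for the latter. These describe who left. None of them corrects or stress-tests the estimated treatment effect.

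**Working it through.** **1. The plan's own sample size.** Inputs from 10.2: difference 4, SD of change 6.76, two-sided 0.05, 80% power, t-test, increases of 50%, 15% and 15%.
- The t-test needs 46 per group, 92 in all.
- 92 × 1.15 × 1.15 = 121.7, which gives the stated 122 for two arms.
- 121.7 × 1.5 = 182.5; rounding up to a multiple of 4 gives the stated 184.

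The figure reproduces, and withdrawal enters it only as a factor of 1.15.

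**2. How many men are left out.**
- 15%: 184 × 0.15 = 27.6, about 28 men (about 7 per arm), leaving about 156.
- 10%: 184 × 0.10 = 18.4, about 18 men, leaving about 166.

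**3. Power.** 156.4 / (1.5 × 1.15) = 90.7, about 45 per group after removing the interaction and clustering factors. Power for 4 points is then about 79%. Power is not the problem.

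**4. Form of the bias.** Let completers on one side of a margin improve by m on average and withdrawers by m − g, with withdrawal fraction p. The all-randomised mean is (1 − p)m + p(m − g) = m − pg, so the completer mean is too high by pg. The bias in the difference, active (A) minus control (C), is p_A·g_A − p_C·g_C. With assumed values:
- Withdrawal of 20% v 10%, same g of 2 to 6 points: 0.10 × 2 = 0.2 to 0.10 × 6 = 0.6 points.
- Withdrawal of 15%, only the active side's withdrawers doing worse by 2 to 6: 0.15 × 2 = 0.3 to 0.15 × 6 = 0.9 points.

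The bias can go either way: in favour of the drug if treated withdrawers do worse, against it if control withdrawers do.

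**5. Simulation.** 92 v 92 (the factorial margins), SD of change 6.76. Assumed, not in the protocol: correlation 0.6 among baseline, week 3 and week 6; lack-of-efficacy dropout depends on week-3 response; side-effect dropout is random. All rows have no true effect; in each the bias runs against the drug.

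| Loss, control v active | Bias (points) | Type I error |
|---|---|---|
| 5% efficacy + 5% side effects v 2.5% + 7.5% | about 0.1 | about 5% |
| 7.5% efficacy + 2.5% side effects v 2.5% + 7.5% | about 0.27 | about 5.7% |
| 10% all efficacy v 10% all side effects | about 0.47 | about 7% |
| about 18% all efficacy v 15% all side effects | about 0.76 | about 11% |

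The error rates follow from bias and standard error. For the last row, 0.76 / 1.06 = 0.72, and P(|Z + 0.72| > 1.96) is about 0.11. Under the extreme mechanism a true effect of 4.0 is estimated as about 3.26.

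A likelihood estimate that also uses baseline and week 3 is close to unbiased in these runs. Its standard error is about 0.93-0.98, against 1.03-1.08 for the completer change. Part of that gain comes from baseline adjustment.

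**The case against.** Several points on the other side are sound.

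- A reader might infer that all of the 15% leave for side effects or lack of efficacy. Section 8.6 does not say so: it ties up to 10% to those reasons and gives the 15% maximum without one.
- A reader might infer that every man who stops treatment is dropped. He is not; if he supplies a week-6 score he is analysed as randomised, and the protocol commits to seeking that score.
- The wording in 10.3 refers to available data, so it can be read as analysis as randomised of whatever scores exist. That softens the contradiction, but a week-3 or early-stop score is also available and has no place in the primary model.
- It would be wrong to say that the plan sees withdrawal only as lost power. It names differential withdrawal as a source of bias and also plans profile models. These remain outside the primary estimate.
- Section 10.3.2 allows methods to be revised in the Data Analysis and Monitoring Plan, which is not at hand. A missing-data rule may be there, so nothing here shows that the final analysis excluded these men. But the protocol does state a primary model, and that model does not fit the label.
- In a 2 × 2 design half of each no-drug margin takes the other active drug. Reasons for leaving are therefore mixed on both sides, and fully asymmetric dropout is unlikely.
- The likelihood model performs well in the simulation partly because dropout was generated from observed week-3 scores, the condition under which it is valid.

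**Conclusion.** The point stands as a mismatch between label and model: the primary analysis, as written, is complete-case and may omit up to about 28 of 184 men. With an assumed correlation of 0.6 and the protocol's SD of 6.76, the simulated bias at roughly the protocol's dropout rates is about 0.1 to 0.5 points on a 4-point target, with a type I error of about 5% to 7%.

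A reader might take about 0.8 points and an 11% error rate as the expected size. The documents do not support that. It needs fully asymmetric losses of 15-18%. Its average loss, (18 + 15)/2 = 16.5%, exceeds the 15% maximum, and its control-side loss for lack of efficacy exceeds the 10% given for both reasons together. All these sizes rest on assumed dropout mechanisms. The sample size itself needs no change.

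**What to change.** In 10.3.2, make the likelihood-based repeated-measures model that is already planned the primary analysis. Use baseline, week 3, any early-stop score at its actual time, and week 6. Include both treatment factors by visit and a centre effect, and name the week-6 contrast as the primary estimate. State the missing-at-random assumption in 10.3. Keep the completer change analysis as a sensitivity analysis, and add one sensitivity analysis for data missing not at random. Clarify how the 10% and 15% in 8.6 relate. If the change-score model stays primary, 10.3 should call it a complete-case analysis.

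The cost is wording in two sections and modest programming; visits and sample size are unchanged. The new primary analysis would rely on missing-at-random given the observed scores, and it gains nothing for men with no post-baseline score.
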